Use of Real Time Instrumentation (RTI) in Total Shoulder Arthroplasty: A Clinical Case Series

NCT01905241

01/10/2014

Use of Real Time Instrumentation (RTI) in Total Shoulder Arthroplasty: A Clinical Case Series

Principle Investigator

[name] [name]

Co Investigators

[name] MD

[name] DO

Study coordinator

[name]

Overall Summary

Glenoid component loosening is the most common complication of total shoulder arthroplasty. Loosening is associated with malposition of the implant as well as the quality of the glenoid bone. Past studies from our research group have addressed these problems by investigating novel surgical technologies to increase the accuracy of glenoid implant placement. Over the course of multiple IRB approved clinical trials, use of our preoperative planning software in combination with patient specific instrumentation (PSI) or intelligent reusable instrumentation (IRI) has proven to more accurately place the glenoid guide pin than conventional standard of care techniques.(Figure 1) (Figure 2)

Continuing our work, we propose a clinical case series to evaluate a new surgical instrumentation technique that combines the features of PSI with the IRI technology that we have termed Real Time Instrumentation (RTI). We will measure implant placement with RSA and 3D CT imaging. We will measure pre-operative bone quality using quantitative CT Scan to measure trabecular bone volume and correlate these findings with bone samples removed from the humeral head and measured by microCT and mechanical testing of the bone samples. This bone tissue is normally removed and discarded as part of the standard of care for preparation of the bone for placement of the humeral head component. We have performed all of the work required to define both the safety of all components of the proposed study in the completed PSI study and the ongoing IRI study. Since application to the IRB for study of the IRI technology Custom Orthopaedic Solutions (Cleveland Clinic NewCo) has received in April 2013 FDA approval for this technology.

Glenoid Instrumentation and Pre-operative planning

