RSA imaging will be obtained at these same points in time. RSA imaging uses biplanar fluoroscopic imaging within a calibration grid and image software to define implant position. This technology has been a standard for precise implant position for the last 20 years and has been used in thousands of patients. RSA imaging uses metallic markers placed in the implant and

in the surrounding bones. The beads implanted in the bone and implant do not move, and are then used as markers to define the location of the implant to the bone and the bones to one another. The accuracy of RSA measurement has been reported to be +/- 0.006mm in translation and 0.5 degrees in rotation. For RSA measurements, a minimum of three 1mm radiopaque tantalum beads into an implant and at least three beads into the surrounding bone when using the RSA system.

Placement of three beads into the implant will also improve the ability of the post-operative 3D CT imaging to define the location of the implant and will be an improvement over our first generation technology. A metal wire is placed in the center peg of the implant by the manufacture of the implant to better identify the implant and its location on post-operative imaging. The three additional beads that we place in the implant will add accuracy to the post-operative imaging.

The risk of the bead becoming loose has been shown to be very small and there is no adverse effects related to bead movement or loosening. We have placed these metallic markers in the glenoid implant (three beads) and in the bone (4-5 beads) in 22 patients to date under the ongoing IRI study. We have not had any problems with bead placement nor any adverse events during or after surgery.

RSA and 3D CT measurements will be correlated and compared. Our goal is to define the accuracy of second generation 3D CT scanning when compared to a gold standard of RSA measurements.

Bone Quality Measurements

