Prior to implanting the glenoid component, three 1mm tantalum beads will be inserted into the backside pegs of the component. We have developed methods to place the beads in a manner that has been used by other investigators and validated in our own experience in 22 cases enrolled in the ongoing IRI clinical study. The desired implant will be placed into a holding device and using a drill guide, a 0.9 mm hole measuring 2 mm deep will be placed in each of the three peripheral pegs of the implant. A 1 mm tantalum bead (RSA biomedical, Umsa Sweden) supplied by the company will then be press fit into the component hole. The implant will then be placed in the glenoid, aligned with the previously drilled peg holes. As standard of care, these peg holes are cemented, thus locking the beads within the implant.

Using manufacturer (RSA biomedical, Umsa Sweden) provided beads and injector gun, four to five 1mm tantalum beads will be placed in the coracoid, acromion and glenoid. Exact placement of these beads is at the discretion of the surgeon. Patient anatomy and operative exposure will guide the surgeon to the best places to inject the beads; however the surgeon will not be confined to a specific amount of beads in a specific location. The beads just need to be spread out amongst the coracoid, acromion, and glenoid to establish reference points for the RSA imaging. Prior studies looking at shoulder joint kinematics and implant position have used this methodology of bead placement with successful study related outcomes. We have successfully placed bone beads in 22 patients currently treated in the ongoing IRI clinical study without any difficulty or adverse events during or after surgery.

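### Bone beads that serve only RSA are placed without condition, although RSA itself is optional (low severity)

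*Combined protocol and SAP*

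**What the plan says.** All references are to the combined protocol and SAP.

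- **RSA described as universal.** The Overall Summary says "We will measure implant placement with RSA and 3D CT imaging". Measurement of Implant Position, having set out the two CT time points, says "RSA imaging will be obtained at these same points in time". Neither mentions an option.
- **RSA described as optional.** Detailed Study Design gives post-operative CT to all patients within three weeks, but RSA only where it was chosen. At two years RSA is repeated only in those who had it the first time. The paragraph on Euclid Hospital patients again makes RSA conditional on choice.
- **Bone beads.** Detailed Study Design says "four to five 1mm tantalum beads will be placed in the coracoid, acromion and glenoid". The surgeon decides where they go and how many go at each site. The stated aim is "to establish reference points for the RSA imaging". Patient Enrollment lists bead placement among the departures from standard care, without reference to RSA.
- **Implant beads.** Measurement of Implant Position gives these a second use: "Placement of three beads into the implant will also improve the ability of the post-operative 3D CT imaging". Data Sheets plans to measure movement of the beads inside the implant and does not mention the bone beads.
- **Risk.** Measurement of Implant Position says "The risk of the bead becoming loose has been shown to be very small" and reports beads placed "in the bone (4-5 beads) in 22 patients to date under the ongoing IRI study". Detailed Study Design adds "We have successfully placed bone beads in 22 patients currently treated in the ongoing IRI clinical study without any difficulty or adverse events".

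**The concern.** The bone beads are a study procedure: they are injected into the coracoid, acromion and glenoid and would not be placed in routine care. Their justification is RSA. Once RSA becomes a choice, the justification holds only for patients who have it, yet the instruction to place the beads does not follow the choice. A surgical team working from the text would place them in everyone.

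What is at stake is a small invasive step with no stated return for some patients. The main results are not at stake. Comparison of component position with the plan (Outcome Measures) and the change between the first and second CT scans (Data Sheets) do not depend on the bone beads. The aim of judging second-generation CT against RSA (Measurement of Implant Position) would rest only on patients who had RSA, and the plan does not give their number. That last point follows from RSA being optional, whatever is done about the beads.

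**Working it through.** The plan gives no figure to reproduce here. The check is mainly a comparison of text, with three short calculations for scale.

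**Text, side by side**

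| Item | Conditional on RSA being chosen? | Stated use |
|---|---|---|
| RSA within 3 weeks (Detailed Study Design) | Yes | Implant position |
| RSA at 2 years (Detailed Study Design) | Yes, only if done the first time | Implant position |
| RSA for Euclid Hospital patients (Detailed Study Design) | Yes | Implant position |
| Three implant beads (Detailed Study Design; Measurement of Implant Position) | No | RSA and post-operative CT |
| Four to five bone beads (Detailed Study Design) | No | RSA only |
| Bead placement as a study change (Patient Enrollment) | No | Not given |

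The surgeon's discretion does not close the gap: it covers the location of the bone beads and the number per site, not whether they are placed. The CT benefit is stated only for the implant beads. The CT comparison described in Detailed Study Design uses the reconstructed scapula and implant and mentions no bone markers.

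**Beads per patient**

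Implant beads 3, bone beads 4 to 5: total 3 + 4 = 7 to 3 + 5 = 8. In a patient without RSA, 4 to 5 of these have no stated use.

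**Patients affected**

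Planned enrolment is 20 (Sample Size). With RSA uptake *u*, the number is 20 × (1 − *u*). The documents do not give *u*, so only bounds are possible: 20 × (1 − 1) = 0 and 20 × (1 − 0) = 20. This assumes that all 20 are retained and that the bead instruction is followed literally. The upper bound requires no RSA at all, which the plan clearly does not expect.

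**What the earlier experience shows**

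- Bone beads placed so far: 22 × 4 = 88 to 22 × 5 = 110, in 22 patients with no reported adverse events.
- One-sided exact 95% upper limit for the per-patient rate with 0 events in 22: 1 − 0.05^(1/22) = 0.127, or 12.7%.

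This limit reflects how few patients have been observed. It is not evidence of harm and does not say how often a patient without RSA would receive bone beads.

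**The case against.** The strongest reply is that the problem depends on one reading of the bead paragraph, and that others are at least as natural.

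1. **The paragraph may be meant only for RSA patients.** It states the RSA purpose, describes the RSA supplier's beads and injector, and does not refer to all patients, a phrase the protocol uses elsewhere for bone samples and CT. This is possible and would remove the problem. But no visible sentence says so, and Patient Enrollment lists bead placement as a change for the series without restriction.
2. **RSA may be meant for everyone**, as the Overall Summary and Measurement of Implant Position read. That also removes the problem, but then the optional wording in Detailed Study Design is wrong and still needs an edit.
3. **The choice may stay open after surgery.** Beads can only go in at operation, so placing them in all patients would keep RSA possible. This is the best argument for the present text. The protocol does not make it, and the window would be short: two-year RSA requires the first RSA, which falls within three weeks of surgery.
4. **The consent form may record the choice and link it to the beads.** Those pages are not in the available copy, so nothing can be concluded from their absence. The point is limited to the operative step as described in the protocol.
5. **Bead movement must be measured against some bone reference**, and Data Sheets does not say which. So bone beads might serve a purpose without RSA. That is an inference; no passage states a CT use for them.
6. **The range of 0 to 20 is uninformative, and no main result changes.** Both are true, and they are why the severity is low.

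The alternative readings limit confidence. They do not remove the mismatch between an unconditional instruction and an optional measurement.

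**Conclusion.** The concern holds, at low severity and with medium confidence. As written, a patient without RSA would receive four to five study-only bone beads for which the protocol states no use.

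This rests on three assumptions: that RSA really is optional, that the bead instruction is followed literally, and that no document outside the available copy ties the beads to the RSA choice. The documents do not say who makes that choice or when. If RSA is universal, or if bone beads are in practice kept for RSA patients, nobody is affected. The stated risk to any affected patient is very small, though the supporting experience is only 22 patients. The CT-based outcomes stand as planned.

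**What to change.** **If RSA is optional:** open the bone-bead paragraph in Detailed Study Design with a condition such as *In patients who chose RSA before surgery*. Keep the three implant beads for all patients, since they have a CT use. Report the CT-versus-RSA comparison with the number of patients who had RSA.

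**If RSA is meant for everyone:** leave the bead paragraph alone and delete the optional wording in Detailed Study Design, both for the early and two-year imaging and in the Euclid Hospital paragraph.

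**If the choice is meant to stay open after surgery:** keep beads for all and state that reason.

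**Cost:** one clause and no new procedure. Under the first option, a patient who declines RSA before surgery cannot change to it later, because the bone markers will be absent.

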We are proposing the first in man use of this technology for placement of the glenoid component in anatomic total shoulder arthroplasty. We will use, as we have for our completed PSI clinical trial and currently active IRI study, post-operative 3D CT Scanning to precisely define the location of the implant as compared to pre-operative plan. We propose to compare the accuracy of implant placement using the RTI - SmartBone technology to the use of IRI and PSI groups as well as the two control groups from these trials. Specifically we are proposing a non-randomized clinical case series. Patients enrolled in this study will be operated on by surgeons involved in the pre-clinical trial and the ongoing IRI study. In all enrolled RTI cases the surgeon will have full control to define the optimal position of the guide pin and the final implant. The surgeon can default to standard of care technology in any case in which the RTI technology cannot be used or results in a guide pin position that in his view is not consistent with the pre-operative plan. Therefore the surgeon is in full control of all intraoperative decision making and execution of the procedure.

In the 60 patients treated in the PSI and IRI study there has not been the need to abort the use of the novel instrumentation, nor has there been a complication during or after surgery relating to the technology. Moreover the objective data of post-operative implant position has proven the PSI and IRI technology to be better than control groups. It is for these reasons that we do not propose to do a randomized clinical trial.

Measurement of Implant Position

Post operatively we will obtain a CT scan with metal artifact reduction technology within the first few weeks after surgery and will generally obtain this scan prior to discharge from the hospital. A second CT scan will be obtained at two years after surgery. We have used these methods of 3D CT imaging to determine implant position in several prior studies. We have defined the accuracy of these measurements using first generation techniques to be within 1 millimeter and 3 degrees. We anticipate that the accuracy of these second generation imaging techniques will be improved from our earlier work.

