To assess bone quality and its effect on glenoid component loosening, we will take trabecular bone samples from all patients. Humeral heads, which are normally discarded as standard of care medical waste will be kept and evaluated with mechanical testing. These bone samples will be assessed by micro CT to measure trabecular bone volume and connectivity as well as by mechanical testing. This data will be correlated with the trabecular bone volume of the glenoid defined by the pre-operative CT scans. In addition all bone quality measurements will be correlated with CT scan imaging of the glenoid at the time of surgery and at two year follow up.

Patient Enrollment

The proposed clinical study will enroll patients indicated for standard of care anatomic total shoulder arthroplasty. They will receive all pre-operative testing, intra-operative care including all implants and post-operative care that is standard of care and specific to the surgeon and patients decisions for care. The only change for the case series will be the type of surgical instruments used to place the glenoid guide pin, coring of the bone to obtain bone tissue, placement of the beads and post-operative CT scanning. In all cases the surgeon is able and allowed to use their own surgical judgment to place the guide pin, prepare the bone and place the desired implant. In all cases, the surgeon can use any and all of the standard instruments or guides provided by the implant manufacturer as the surgeon would use if the patient was not enrolled in the study. If the surgeon chooses not to use the RTI technique then this would be noted as a deviation in plan, the reasons recorded and the patient would be excluded from the study without post-operative imaging and their pre-operative and intra operative data would be

analyzed for the purpose of understanding the reasons for failure of the RTI technology to provide assistance for refinement of the technology.

Detailed Study Design:

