The study will enroll 20 patients directly into the RTI group. We will have two surgeons with experience in shoulder arthroplasty and the RTI and SmartBones technology. We will require a minimum of five patients from any one surgeon. All patients will have the standard of care indications for an anatomic total shoulder arthroplasty and will give informed consent for both the surgery and participation in this study. Consent and enrollment will be obtained by the surgeon during a routine office evaluation. All patients will get standard of care pre-operative x-rays and CT scan at least three weeks prior to surgery. Scan quality must meet study specific criteria and we expect that the scans will be performed at the Cleveland Clinic. The pre-operative CT scan will be placed within our pre-operative planning software (OrthoVis Cleveland Clinic). The surgeon will use this software to assess the glenoid bone pathology and select the optimal implant and placement of that implant.

Patients will have standard of care indications for primary anatomic arthroplasty and be able to get a pre-operative shoulder CT scan at the Cleveland Clinic or at an outside facility so long as the study includes the entire scapula and has 1mm or thinner sections. These parameters are required for accurate pre-operative planning as well as comparison with the post-operative CT scans. Standard of care pre- and post-operative x-rays (AP and axillary views) will also be obtained and can be performed at the Cleveland Clinic or acquired from another health care facility. In all patients the standard x-rays and CT images provided by the radiology department will be available to the surgeon before and during the surgery.

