properly determine the quality of the bone stock surrounding the implant. Further correlating this with RSA and 3D CT imaging of implant movement, we can fully develop cause and effect of bone quality on glenoid component loosening.

The participating surgeons will be [name] and [name]. Patients may have surgery at either Cleveland Clinic main campus or at Euclid Hospital. If the procedure is performed at Euclid Hospital, post-operative CT scan and RSA (if chosen), will need to be taken at main campus within 3 weeks. The patient will be made aware of this at the time of enrollment and consent.

Inclusion/Exclusion Criteria:

To be eligible for inclusion, a primary anatomic total shoulder arthroplasty must be indicated for the patient.

Outcome Measures:

By comparing computer generated pre-operative plan to post op component placement, we will be looking at three outcomes. First, the overall difference in component placement between standard of care instrumentation, intelligent reusable instrument (IRB#12-997), patient specific instruments (IRB #10-582) and real time instrumentation will be compared. Secondly, we will compare the placement between the technologies within and between surgeons. Thirdly, we will evaluate the difference in implant position between technologies based on severity of pathology. The quality of the bone core sampled will be correlated to the possible loosening of the implants.

Sample Size:

We expect to enroll 20 patients for this clinical case series. Data collected will be analyzed in association with the enrollees from IRB#12-997 and IRB#10-582.

Statistical Methods

Average deviations from plan for the RTI, IRI, and freehand groups will be compared using mixed-effects ANOVA methods. Random effects will be included to account for correlation between observations introduced as a consequence of multiple observations of deviation being taken on a particular surgeon. If significant differences are found, multiple comparisons based on the ANOVA model will be made to compare each pair of groups, and will use Holm's step-down procedure to control the family-wise error rate of the tests.

All analyses will be done using R software (version 3.0.0, Vienna, Austria). A significance level of 5% will be used for all testing.

Data Sheets

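### The protocol claims it can establish cause and effect of bone quality on glenoid loosening, but the design supports only an exploratory association

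*Combined protocol and SAP*

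**What the plan says.** The causal statement closes the account of imaging and bone testing in Detailed Study Design. Pre-operative imaging and tissue analysis together are said to "properly determine the quality of the bone stock surrounding the implant". The next sentence begins "Further correlating this with RSA and 3D CT imaging of implant movement" and concludes that "we can fully develop cause and effect of bone quality on glenoid component loosening".

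Elsewhere the same work is described only as correlation. Outcome Measures says "The quality of the bone core sampled will be correlated to the possible loosening of the implants". Bone Quality Measurements plans to correlate the tissue results with glenoid trabecular bone volume from the pre-operative CT, and all bone measures with glenoid CT at surgery and at two years. It gives the tissue source: "Humeral heads, which are normally discarded as standard of care medical waste will be kept and evaluated with mechanical testing".

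On design, Glenoid Instrumentation and Pre-operative planning states "Specifically we are proposing a non-randomized clinical case series". Detailed Study Design states "The study will enroll 20 patients directly into the RTI group", and Sample Size repeats the number: "We expect to enroll 20 patients for this clinical case series". Sample Size adds that the data will be analysed together with enrollees of two earlier studies.

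Statistical Methods covers only deviation from plan between instrumentation groups, by mixed-effects ANOVA. It contains no term or model for bone quality. Data Sheets plans to correlate change in implant position with seating, type of implant, joint-line medialisation, perforation of pegs and severity of pathology.

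**The concern.** The protocol states a causal conclusion as something the data will deliver. Nothing in the plan provides for it: no assignment of the exposure, no model, no adjustment set and no stated causal assumptions. The protocol itself lists other factors that may go with implant movement. If the sentence stands, a correlation in about 20 people could be reported as showing that poor bone causes loosening.

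A smaller issue goes with it. The one bone-quality statement in Outcome Measures names the bone core. The only tissue source that the protocol names is the humeral head, whereas the implant sits in the glenoid. Of the planned measurements, only the glenoid CT measures the bone around the implant directly.

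**Working it through.** **Is there a figure to reproduce?** No. The 20 patients are not derived from an effect size, standard deviation or power, so no stated number is tested and none is called wrong.

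**Step 1: claim against design.**

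| Needed for a causal conclusion | What the documents give |
|---|---|
| Exposure assigned, or confounding controlled | Bone quality is measured as it occurs; no adjustment stated |
| A specified analysis with its assumptions | Correlation only; Statistical Methods is silent on bone quality |
| Competing explanations handled jointly | Data Sheets correlates several factors with movement; no joint model stated |

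**Step 2: why a larger sample would not help.** Suppose a factor U correlates a with bone quality and b with movement, and bone quality has no effect on movement. Under a linear model the correlation between bone quality and movement is then r = a × b. With assumed values a = b = 0.6, r = 0.6 × 0.6 = 0.36. Approximate power to declare this non-causal correlation significant is Φ(atanh(r)·√(n−3) − 1.96):
- n = 20: Φ(0.377 × 4.123 − 1.96) = Φ(−0.41) = 0.34
- n = 200: Φ(0.377 × 14.04 − 1.96) = Φ(3.33), above 0.99

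More patients make the spurious result more certain to appear. The 0.6 is illustrative; with 0.5 or 0.7 the induced r is 0.25 or 0.49.

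**Step 3: precision at n = 20.** Inputs: n = 20 (Sample Size); 5% level (Statistical Methods), taken as two-sided because sidedness is not stated; Pearson correlation assumed.
- Smallest significant |r| = t/√(n−2+t²), with t = 2.101 on 18 degrees of freedom: 2.101/√(18 + 4.414) = 0.44.
- 95% interval = tanh(atanh(r) ± 1.96/√17), where 1.96/√17 = 0.475. For r = 0: −0.44 to 0.44. For r = 0.3: −0.16 to 0.66. For r = 0.5: 0.07 to 0.77.
- Correlation detectable with 80% power = tanh((1.96 + 0.842)/√17) = tanh(0.680) = 0.59.

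**Step 4: could n differ from 20?** It may be lower. RSA is optional, quantitative CT is used only when available for Main Campus patients, and a patient whose pin is changed without the RTI gets no post-operative CT. The documents give no numbers for these losses. At an assumed 15 or 10 usable patients, the smallest significant |r| is 0.51 or 0.63.

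It could be higher only if the earlier enrollees had the same measurements, which the documents do not show. With all 60 earlier patients, n = 20 + 60 = 80 and the correlation detectable with 80% power is tanh(2.802/√77) = 0.31. Step 2 would be unchanged.

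**The case against.** The strongest reply is that this is one loose sentence in the narrative. Cause and effect appears once, it is not among the three numbered outcomes, and no test in Statistical Methods serves it. Outcome Measures and Bone Quality Measurements already speak of correlation. This stands as a limit on the point: what needs correcting is a stated conclusion, not the trial's structure. It does not remove the point, because the sentence says what the bone-quality work will conclude, no analysis section tempers it, and the aim is nowhere called exploratory.

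Pooling with the earlier studies might also be offered in reply. It could help precision if those patients had bone-quality data, but it would not address confounding.

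A reader might infer more than the documents support:

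- *That the protocol itself calls malposition a cause of loosening.* Overall Summary says only that loosening is associated with malposition, and it names glenoid bone quality in the same sentence.
- *That the plan relies on humeral tissue alone.* The sentence about bone around the implant rests on imaging as well as tissue, and Bone Quality Measurements links the tissue results to glenoid CT. The gap is confined to the Outcome Measures sentence.
- *That the plan commits to an unadjusted analysis.* It specifies no bone-quality model of either kind. Several competing factors are collected and examined, although no joint adjustment is stated.

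**Conclusion.** The concern holds as an over-claim. A correlation between observed bone quality and implant movement, in one non-randomised group with a documented maximum of 20, supports an association. As specified it does not support cause and effect at any sample size. That conclusion rests on the design and needs no numerical assumption.

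The imprecision is secondary. At n = 20 only correlations beyond about ±0.44 reach significance, and about 0.59 is needed for 80% power (two-sided 5%, Pearson correlation). The figures for 15 and 10 patients and the confounder of 0.6 are assumptions for scale.

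It would be wrong to read the small sample as the reason the causal claim fails, or to conclude that the placement comparison, its model or the enrolment target is affected. The correction is worth making because it changes what the study may conclude about bone quality.

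**What to change.** 1. In Detailed Study Design, replace the causal sentence with: *we will estimate the association between bone quality and implant movement, with 95% confidence intervals, as exploratory.*
2. In Outcome Measures, name the glenoid bone measure obtainable from every patient's pre-operative CT, with quantitative CT where available, alongside the humeral-head microCT and mechanical results. Quantitative CT cannot simply be made the main exposure, because it will be absent for an unknown number of patients. State also which movement measure is used.
3. If an adjusted sensitivity analysis is added, use one pre-operative factor already listed in Data Sheets, such as glenoid bone loss or version. Do not adjust for back side contact or deviation from plan. Both arise at surgery, after bone quality is fixed, and may lie on the path from bone quality to movement, so adjusting could remove part of the association of interest. With 20 patients such an analysis is a check on robustness and does not make the result causal.

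The cost is a few sentences, plus a decision on which CT bone measure all patients can supply. No new data collection is needed if that measure can be taken from the planned scans. The downside is a more modest stated aim.

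### RTI is wholly confounded with study: the model has no study term and a single freehand label, so any between-study difference is tested as an RTI effect

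*Combined protocol and SAP*

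**What the plan says.** - **Design** (Glenoid Instrumentation and Pre-operative planning): "Specifically we are proposing a non-randomized clinical case series". RTI is to be compared with the IRI and PSI groups "as well as the two control groups from these trials", so two standard-of-care control groups are in view.
- **Allocation** (Detailed Study Design): "The study will enroll 20 patients directly into the RTI group". There is no concurrent control.
- **Sample Size:** "We expect to enroll 20 patients for this clinical case series", followed by "Data collected will be analyzed in association with the enrollees from IRB#12-997 and IRB#10-582".
- **Model and tests** (in the Statistical Methods section): the model sentence reads "Average deviations from plan for the RTI, IRI, and freehand groups will be compared using mixed-effects ANOVA methods". The only random effects described are for repeated observations on the same surgeon. If the overall test is significant, pairwise comparisons follow and "will use Holm's step-down procedure to control the family-wise error rate of the tests". Then: "A significance level of 5% will be used for all testing".
- **Not found:** a study, period or imaging-generation term, a statement of which patients make up the freehand group, or a check that the two control groups agree. PSI is a comparator under Outcome Measures but is absent from the model sentence.

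**The concern.** Technique and study cannot be separated for RTI. Whatever differs between this study and the other two enters the RTI contrast as if the instrument had caused it, and it is missing from the standard error behind the test.

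The protocol itself gives reasons to expect some difference. Measurement of Implant Position expects second-generation imaging to be more accurate than in earlier work, and expects beads in the implant to add accuracy. Patient Enrollment and Detailed Study Design exclude patients in whom RTI is not used, or whose pin is moved without it. No matching rule is described for the comparator studies.

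At stake is how a significant RTI v freehand result would be read. A Holm-adjusted p-value at 5% looks like evidence about the instrument, when part or all of it could be a study difference of unknown sign. A single freehand level would also hide the one place where the same control label appears in two studies. It would also draw IRI, which has controls in its own study, into the cross-study problem.

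**Working it through.** **The plan's own figure.** N = 20 comes with no effect size, SD or power, so there is nothing to reproduce.

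**Inputs from the protocol.** 20 RTI patients; groups RTI, IRI and freehand; two control groups, one in each comparator study; surgeon random effects only; overall test, then Holm at 5%.

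**Assumptions not in the protocol.** Two-sided tests; 15 IRI and 15+15 controls (the protocol gives 60 patients across the PSI and IRI studies without a split by arm); patient SD = 1; independent study effects with SD τ = 0.2 to 0.3; no surgeon effect; freehand pooled.

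**1. Would a study term separate RTI from study?** With an intercept, two group indicators (IRI, RTI) and two study indicators, the design has 5 columns. The RTI column equals the column for this study, so the rank is 4. RTI minus freehand is not estimable, while IRI minus freehand is. If freehand means only the #12-997 controls, there are 4 columns of rank 3 and the conclusion is the same.

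**2. Standard error of RTI minus pooled freehand.**
- Planned model: √(1/20 + 1/30) = √0.0833 = 0.289 SD.
- With study effects: √(0.0833 + τ²(1 + 0.5² + 0.5²)) = √(0.0833 + 1.5τ²).
- τ = 0.2: √(0.0833 + 0.060) = 0.379 SD.
- τ = 0.3: √(0.0833 + 0.135) = 0.467 SD.

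**3. False rejection of RTI v freehand** (simulation, 40,000 runs)

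| τ | Unadjusted 5% two-group test | Overall F-test, then Holm over three pairs |
|---|---|---|
| 0 | 5% | under 2% |
| 0.2 | 13% | about 7% |
| 0.3 | 22% | about 14% |

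The right-hand column is the planned procedure.

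**4. IRI minus freehand.** Against pooled controls, the planned SE is √(1/15 + 1/30) = 0.316. With study effects it is √(0.100 + 0.5τ²) = 0.346 at τ = 0.2 and 0.381 at τ = 0.3. An unadjusted 5% test then errs in roughly 7 to 10% of runs. Against the #12-997 controls alone the study effect cancels and the error stays at about 5%.

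**5. What the two control groups can show.** Their difference has SE √(1/15 + 1/15) = 0.365 SD. At τ = 0.2 to 0.3 it reaches p < 0.05 in only about 12 to 20% of runs.

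**6. Price of separate control levels.** The SE of RTI minus one control group is √(1/20 + 1/15) = 0.342, and 0.342/0.289 = 1.18.

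**The case against.** The protocol is open about being a non-randomised series and gives its reasons. RTI surgeons are also involved in the IRI study, so the surgeon effect has some overlap to work with. Study #12-997 is ongoing, so its controls may be close in time. Detailed Study Design says the CT position measurement was validated in #10-582. All of this stands and limits how large a study effect is plausible. None of it addresses differences other than surgeon, and a declared design does not change how the pairwise p-values will be read.

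Four stronger readings are tempting, and the documents do not support them.

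- **That the plan's error rate is 13 to 22%.** That is an unadjusted test. The overall test and Holm bring it to about 7 to 14%, and both ranges depend on an assumed τ.
- **That the plan pools the controls.** One label for two groups suggests it, but since PSI is missing from the model sentence, freehand could mean the #12-997 controls only. Nothing would then be pooled. RTI would still be confounded with study, and the second control group would go unused.
- **That planned confidence intervals are too narrow.** Statistical Methods speaks of tests and mentions no intervals.
- **That the control-v-control difference is a free estimate of the shift affecting RTI.** It compares #10-582 with #12-997 and says nothing direct about this study's own shift. It is one imprecise draw. The documents also do not show that planning and imaging were the same for both control groups, so it need not reflect drift alone.

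**Conclusion.** The confounding and the missing study term follow directly from the protocol and need no assumption. The size is illustrative: under the assumptions above, the planned procedure falsely rejects RTI v freehand in about 7 to 14% of runs, against under 2% with no between-study difference. Inflation requires τ above zero. The imaging changes and RTI-specific exclusions make that plausible, but the documents do not give its size or show that drift has occurred.

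No modelling choice removes the problem: a fixed study term makes the RTI contrast non-estimable, and a random one would rest on three studies. What can be improved is how the contrasts are built and labelled. This is a cheap improvement, not a reason to redesign the study.

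**What to change.** In Statistical Methods:

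1. State which patients form the control groups, and keep the #10-582 and #12-997 standard-of-care controls as separate levels.
2. Compare IRI with the #12-997 controls.
3. Report RTI minus each control group with 95% CIs.
4. Report the difference between the two control groups with its CI, as an imprecise descriptive indicator of between-study differences (SE about 0.37 SD at 15 per group). Do not use it as a pass/fail test, and state that it can neither identify nor remove this study's own shift.
5. Label every RTI contrast non-randomised, cross-study and not confirmatory, and restate which comparisons remain in the Holm family.

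Requiring both RTI-control contrasts to point the same way is not worth adding. In simulation, imposed on the unadjusted pooled test, it left the error essentially unchanged: 13.0% to 13.0% at τ = 0.2, and 21.6% to 21.5% at τ = 0.3.

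The cost is SAP wording and one extra contrast. Each separate RTI-control interval is about 18% wider than the pooled one (SE 0.34 v 0.29 SD). That widening reflects the smaller control group only and contains no allowance for drift, which is why the label in item 5 is needed.
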